1. PROTOCOL SUMMARY

Title: Topical Ruxolitinib (Jak1/Jak2 inhibitor) in Chronic Hand Dermatitis attenuates inflammation and enhances skin barrier repair.

Principal Investigator: [name] [name];
[contact]

Single site: Department of Dermatology - University of Rochester Medical Center, Rochester, NY

Study phase: Open label, proof of concept study

Population: Females and Male, age 18 - 75 years, who have moderate to severe Chronic Hand Dermatitis (CHD)

Number of participants: Up to 25 will be enrolled with 15 completing full study term

Intervention: Ruxolitinib cream 1.5% is an investigational drug that will be applied twice daily (BID) for 12 weeks (IND exempt) by the study participant. Ruxolitinib (Other Name: INCB018424) cream is a topical formulation applied as a thin film to affected areas.

Objectives and Endpoints:Primary objective & outcome:

1. To assess the efficacy of Ruxolitinib cream 1.5% on skin lesions in patients with Chronic Hand Dermatitis:

- proportion of patients achieving an Investigators Global Assessment (IGA) score of 0 or 1 with at least a 2-step improvement (IGA treatment success) at week 12
- Hand Eczema Severity Index (HECSI)-75% from baseline to week 12

Secondary objective & outcome:

- To assess the efficacy of Ruxolitinib cream 1.5% on other clinical domains:
Time to IGA treatment success
- Change in HECSI score from baseline to week 4, 8 and 12.
- Proportion of subjects with a ≥ 2 and ≥ 4 -point improvement in Itch Numerical Rating Scale (NRS) score from baseline to week 12.
- HECSI-75% at week 8
- HECSI-90% at week 12

2. To assess safety and tolerability of Ruxolitinib cream 1.5% in patients with chronic hand dermatitis:

- incidence, frequency and severity of adverse events and laboratory data for hematology, serum chemistry and urinalysis
- use of rescue medications

Exploratory objective & outcome:

1. To assess the effect of Ruxolitinib cream 1.5% on patient reported outcomes
 - Change from baseline to week 4, 8 and 12 in DLQI
 - Change from baseline to week 4, 8 and 12 in work productivity and activity impairment index
2. To assess the efficacy of Ruxolitinib cream 1.5% on skin barrier integrity in patients with Chronic Hand Dermatitis:
 - change in transepidermal water loss (TEWL) and barrier integrity score (TEWL recovery after tape stripping) and pH from baseline to week 4 and end of treatment on perilesion (normal appearing) skin
3. To identify translational skin biomarkers

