4. STUDY TREATMENT & DESIGN

Study design: This is an open label, proof of concept single site study and will be conducted at the Department of Dermatology, URMC

- Screening visit (-28 days before start of treatment)
- visit 1 - (V1, day 0), start of active treatment;
- visit 2 – 28 +/- 3 days (4 weeks) treatment;
- visit 3 – 56 +/- 3 days (8 weeks) treatment;
- visit 4 – 84 +/- 3 days (12 weeks) end of treatment
- visit 5 – 112 +/- 3 days (16 weeks) safety follow up 4 weeks post treatment
- during each visit a skin swab will be collected and stored in the lab for future microbiology study
- Skin Symptom questionnaire will be done during each visit.

Screening visit (-28 days)

- 1) Consenting and confirmation of inclusion & exclusion criteria
- 2) Medical history
- 3) Physical exam with focus on skin exam
- 4) Collection of concomitant medications
- 5) Fasting blood draw for safety labs (CBC with diff, Chemistry, Lipid panel)
- 6) Urinalysis
- 7) Possible washout period

- 8) Possible schedule PATCH test if investigator believes clinically necessary to r/o contact dermatitis
- 9) Urine Pregnancy test for woman of childbearing potential
- 10) Scheduling visit 1

Visit 1 (Day 0):

- 1) Confirmation of inclusion & exclusion criteria
- 2) General history
- 3) Physical exam
- 4) Review of concomitant medications
- 5) Urine pregnancy test for woman of childbearing potential at each visit. Counseling on acceptable birth control measures to use throughout treatment period including 30 days after stopping study drug (16 weeks or 112 days)
- 6) Clinical scores for chronic hand dermatitis
- 7) Itch and other QoL assessments; review daily diary
- 8) Digital pictures of the target area/hands
- 9) Non-invasive skin barrier Measurements: TransEpidermal Water Loss (TEWL) and optional pH may also be performed
- 10) Repeated tape stripping (Cuderm™ tape) of peri-lesional (0, 5, 10, 15, 20 tape) locations from treated area will be collected as part of the TEWL assessment and to assess for SC cohesion/integrity (rate of change in TEWL with repeated stripping). Serial measurements of TEWL will be performed after tape stripping as previously described^{vii}. This will also allow collecting proteins (eluted from the tape) for validation of biomarkers
- 11) Dispense Investigational drug for 4 weeks
- 12) Provide instructions to complete at home diary.
- 13) Provide date of Visit 2
- 14) Weight of the tube to check for subject's compliance
- 15) Skin swabs (optional)

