- 16) Skin symptom questionnaire (optional)

Visit 2 (Day 28 +/-3) and Visit 3 (Day 56 +/-3) and Visit 4 (Day 84 +/-3):

- 1) Review subject diary and address any questions, concerns, or missed doses
- 2) Review of concomitant medications
- 3) Adverse events assessment
- 4) Questionnaire to clinically characterize CHD
- 5) Urine Pregnancy test for woman of childbearing potential.
- 6) Clinical score for CHD
- 7) Itch and other QoL assessments, review daily diary

- 8) Digital pictures of the targeted area
- 9) Non-invasive skin barrier Measurements: transepidermal water loss. Optional: pH
- 10)Repeated tape stripping (Cuderm™ tape)
- 11)Dispense investigational drug for following 4 weeks (except Visit 4, end of treatment)
- 12)Review Diary instructions
- 13)Weight of the tube to check for subject's compliance
- 14)Provide date for next visit
- 15)Skin swabs (optional)
- 16)Skin symptom questionnaire (optional)

Visit 5 (Day 112 +/-3):

- 1) Review subject diary and address any questions, concerns, or missed doses
- 2) Review concomitant medications
- 3) Adverse Events Assessment
- 4) Questionnaire to clinically characterize CHD
- 5) Urine Pregnancy test for woman of childbearing potential.
- 6) Clinical score for CHD
- 7) Itch and other QoL assessments; review daily diary
- 8) Digital pictures of the targeted area
- 9) Non-invasive skin barrier Measurements: transepidermal water loss. Optional: pH and skin swab
- 10)Repeated tape stripping (Cuderm™ tape)
- 11)Weigh returned tubes

Unscheduled Visit(s)

Any follow-up assessment that is performed to monitor a subject will be collected as an unscheduled visit. The study team is responsible for review of any side effects, concomitant medications, and a brief physical examination. The remaining elements of the unscheduled visit are up to the discretion of the investigator and may include any of the events listed in Visits 1 through Visit 5.

Study procedures & methods

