- **Skin barrier measurements:** Transepidermal water loss/TEWL, +/- pH will be obtained on treatment area at a perilesional site. This measurement asses the dryness and health of the skin. For each of the specific measurements, a probe will be gently applied on the skin surface for up to 1 minute. We will perform all measurements in a climate-controlled examination room with consistent temperature (~23°C) and humidity (~50%). The patient must be very comfortable in the room in which they are being tested to ensure that perspiration due to stress

or acclimatization does not alter the TEWL. TEWL will be assessed using a non-invasive skin probe that measures skin hydration - or other similar device available in the CTU. The URMC department of Dermatology owns the devices and has experience with measurements. **Stratum Corneum (SC) integrity:** the most superficial layers of the skin will be collected by tape stripping using D-squame (D-squame®, CuDerm, Dallas TX, USA). This is a well-established method used in clinical research to gently perturb the skin barrier. The first tape will be discarded to eliminate dirt and remnants of skin products. Each tape will be gently pressed against the skin with standardized pressure for 5-10 seconds (sec) using a standardized pressurizer (D500–D-squame® pressure instrument, CuDerm)). All subjects will have 20consecutive tapes collected from lesional skin as part of this study. TEWL will be measured after each set of 5 tape strippings. These measurements should provide data to determine if the treatment has an effect on skin barrier integrity. Dsquame tapes will be collected and stored in -80 C freezer (see below). Expression of relevant biomarkers can be investigated using RNA or protein eluted from the tapes. [name] lab is familiar with the methods and analysis

- **Skin swab:** will be collected at each visit. Briefly a sterile swab will be rolled on the dorsal hand (non-dominant hand) at each visit and stored at -80C for future analysis

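### The protocol contradicts itself on the tape-stripping site for the exploratory barrier integrity score: lesional skin in one methods sentence, perilesional skin in the objective, the hypothesis and Visit 1

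*Combined protocol and SAP*

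**What the plan says.** Exploratory objective 2 appears in Section 1 and again in Section 6. It takes the change in TEWL, barrier integrity score and pH "from baseline to week 4 and end of treatment on perilesion (normal appearing) skin". The hypothesis in Section 2 (Design & Methodology) likewise concerns normalising the barrier of perilesional skin.

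Section 4 describes the procedure in three places:

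- **Visit 1, item 10.** Tape stripping is "of peri-lesional (0, 5, 10, 15, 20 tape) locations from treated area", done as part of the TEWL assessment. The item adds: "This will also allow collecting proteins (eluted from the tape) for validation of biomarkers".
- **Visits 2–4, item 10, and Visit 5, item 10.** Each gives only "Repeated tape stripping (Cuderm™ tape"), with no skin site.
- **Study procedures & methods.** The skin barrier text says that TEWL "will be obtained on treatment area at a perilesional site". The stratum corneum integrity text that follows says: "All subjects will have 20consecutive tapes collected from lesional skin as part of this study". It continues: "TEWL will be measured after each set of 5 tape strippings", and then: "These measurements should provide data to determine if the treatment has an effect on skin barrier integrity".

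**The concern.** The barrier score is a within-subject change from baseline, so the endpoint has meaning only if the readings come from the site it names and from the same kind of skin at each visit. The methods paragraph, where staff would look for the technique, sends the whole stripping procedure to a different kind of skin from the one in the objective. Barrier repair is in the trial's title and central hypothesis, so although the outcome is exploratory, it is the mechanistic result that readers will look for. A session done at the wrong site cannot be repeated later.

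**Working it through.** No sample size, power or event count is involved. The check sets side by side every statement that names a site for TEWL or tape stripping.

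**1. Do the two descriptions concern the same procedure?** The methods paragraph gives 20 tapes with TEWL after each 5, so 20 / 5 = 4 post-stripping readings, at 5, 10, 15 and 20 tapes. Adding the unstripped reading gives 4 + 1 = 5, which is the 0, 5, 10, 15, 20 sequence in Visit 1 item 10. Tape count and reading schedule agree; only the skin site differs.

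**2. Could lesional be a loose name for the treated area?** Section 2 says the cream goes on the eczematous areas of the hands and on the adjoining clinically normal skin, which it calls perilesional. It also explains why the normal-appearing skin was included. Both areas are treated, but the protocol keeps them apart by name.

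**3. Could the lesional tapes be a separate biomarker series?** The biomarker objective (exploratory objective 3) names no site, so this is worth testing. But the methods paragraph ties TEWL to the lesional tapes and gives barrier integrity as the purpose of those readings. Visit 1 draws biomarker protein from the perilesional tapes. No text describes a second series.

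**4. Do the visit lists settle the site?** The endpoint uses baseline (Visit 1), week 4 (Visit 2) and end of treatment (Visit 4). Visit 1 names the perilesional site. Visits 2 and 4 name none, so for those visits the reader is left with the methods section, where the TEWL sentence and the tape sentence disagree.

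**5. What follows under each way of carrying it out?**

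- *All visits perilesional:* the endpoint is measured as stated, and the methods sentence is simply wrong.
- *All visits lesional:* all 4 post-stripping readings in each session are off the endpoint's site. The change then describes treated eczema, not normal-appearing skin.
- *Visit 1 perilesional, later visits lesional:* the change from baseline compares normal-appearing skin with lesional skin, so a difference between sites is mixed with any treatment effect.

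The documents do not say which would happen, so neither a number of off-site readings nor a size of bias can be derived.

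**The case against.** The strongest reply is that this is a drafting slip, lesional written for perilesional. The objective, the hypothesis, the only visit list that names a site and the neighbouring TEWL sentence all agree, and the measurements are made in a single department experienced with them. That is plausible, though the documents cannot prove it. It is a reason to correct the sentence, not to leave it: the sentence is an operative instruction applying to all subjects, and the later visit lists do not override it.

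A reader might go further and infer that the plan as a whole measures the barrier score at the wrong site. The documents do not support that, because Visit 1 item 10 matches the endpoint. The protocol is inconsistent, not uniformly lesional.

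A reader might also infer that the result would reflect lesion healing, or that a single stripping curve would mix sites. The first holds only if staff follow the methods sentence at every visit. The second needs the further assumption that the perilesional TEWL sentence covers only the unstripped reading, a limit that sentence does not state. The absence of a control arm does not create the problem either: a perilesional change would be just as uncontrolled.

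It is also fair to say that the intended site for biomarker tapes is not established. Some lesional sampling may have been wanted, and the fix should leave room for it.

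**Conclusion.** The contradiction stands. It is a conflict in the text over measurement site, with no reconciling statement, and it should be corrected. Its reach is limited to the exploratory barrier integrity score and, indirectly, to biomarkers taken from the same tapes. The IGA and HECSI primary endpoints and the safety outcomes are not affected. The harm is conditional: it arises only if the methods sentence is followed at some or all visits.

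This conclusion assumes that the methods paragraph and Visit 1 item 10 describe one procedure, which the matching tape counts and reading schedule support.

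The objective's description of the score as TEWL recovery, against Visit 1's description of a rate of change with stripping, is a separate matter of definition and is not part of this point.

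**What to change.** - In the stratum corneum integrity paragraph of Section 4, replace the reference to lesional skin with the perilesional (normal-appearing) treated site named in exploratory objective 2 and Visit 1.
- State that same site in item 10 of Visits 2–4 and in item 10 of Visit 5.
- If lesional tapes were also intended for biomarkers, define them as a separately labelled series and say that they are not used for the barrier score.

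The first two changes touch one methods sentence and two visit-list items and add no visits or tapes. Nothing is lost against the Visit 1 plan, which already takes biomarker protein from the perilesional tapes. Only the third change has a cost beyond wording, namely extra tapes at the visits where lesional material is collected.

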Qualified and enrolled subjects (see Inclusion/exclusion criteria) will be required to come to URMC Dermatology Clinic for at least five visits: visit 1 (V1, day 0), start of active treatment; visit 2 - 4 weeks treatment; visit 3 – 8 weeks and visit 4 – 12 weeks and end of the active study; visit 5 post treatment follow up, 4 weeks (V5, 112+/- 3 days post V1). To ensure feasibility of enrollment, and in subjects requiring a washout period, we will include a screening visit (up to 28 days +/- 3 prior to V1). As part of the screening, subjects with possible contact allergy dermatitis (CAD) will undergo PATCH testing (70 common allergens, North America series; see *exclusion criteria*) or they must have documentation of test performed 3 years prior screening. In patient with CHD avoidance of the allergens should be the first measure to ensure successful treatment. Subjects with known antigen sensitization based on Patch test (with 3 years) that are unable to reduce contact with the specific antigen(s) will be excluded.

We will also exclude patients with active lesions of Atopic Dermatitis and Psoriasis (see *exclusion criteria*), as they might need additional systemic or topical treatment that could indirectly affect hand dermatitis severity during the study.

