- **Study Drug Diary:** subjects will be provided with a prepopulated dated calendar to record their twice daily (AM and PM) application of study medication as well as the time the medication is applied. Also, on this diary the subject can indicate if a missed dose occurred and there is a blank space they can write in the reason it was missed. At the END of each day the subject will need to indicate on the same study diary their level of hand dermatitis itch throughout the day – 0=no itch and 10=worst imaginable itch. Subjects will indicate their level 0-10 by circling the number that best applies to them for that particular date. Detailed instructions are provided on the Incyte Study Diary as well as contact information of coordinator.

Prohibited Medications and procedures: use of topical or systemic immunosuppression/immunomodulators medications and Phototherapy is not permitted during the study. Hand surgery or other procedures (including but not limited to Cryotherapy, ED&C, skin biopsy) are disallowed during the study. If medically necessary, the investigator will withdraw the patients from the study.

5. RISK, BENEFITS and PROTECTION AGAINST RISKS

Risks Associated with Digital Picture

There are no known risks for the digital picture. The image will not include identifying features and will be labeled with study subject ID and date. ~~Pictures will be taken with a dedicated camera, stored on a secure server.~~ Pictures will be taken through the Haiku App and stored in the patients EMR in Epic.

Risks Associated with Barrier Assessments

There are no known risks for the barrier assessments.

Risks Associated with Tape Stripping

The risks associated with tape stripping, theoretically, include the rare possibility of an allergic reaction to the tape and infection. Since the tape is removed immediately after application, the risk of reaction is extremely low. In previous and ongoing studies involving tape stripping, it has been noted that a very mild erythema may develop immediately after a series of tape stripplings on one localized area of skin, presumably due to the mild mechanical disturbance. The erythema is expected to resolve within 12 hours without sequelae. The risk of skin infection is extremely low since only superficial skin layers are removed. Subjects will be provided with wound care information and a department phone number to contact should they have any concerns.

Risks of Phlebotomy

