The risks of having blood drawn include some pain when the needle goes in, and a small risk of bruising and/or infection at that site. Some people will get lightheaded, nauseous, or faint. Approximately 3 teaspoons of blood will be drawn and is not likely to cause lightheadedness, however subjects will be observed after blood draw to be sure they are comfortable with ambulation. Subjects will be encouraged to drink plenty of water prior to the blood draw. Phlebotomy will be performed at the antecubital fossa to minimize pain and bruising. Subjects will be seated during the blood draw to minimize dizziness and any risk of falling. Pressure will be applied to the site after the draw and a band-aid will be applied to minimize the risk of bleeding and infection. Fasting laboratories will be processed at URMC local lab. We require fasting laboratories as the lipid panel can be influenced by food intake and it is routine care to do fasting laboratories of at least 6 hours. Due to known side effects of systemic class of medication we want to screen patients for leucopenia, high lipids, liver or kidney diseases; normal or non-clinical significant labs at baseline are useful to rule out these problems and can be helpful in case we have side effects during the study.

The clinical trial team will receive and review the laboratory results between 24-48 hours.

Risks of Ruxolitinib 1.5% cream

Skin-related side effects of ruxolitinib cream are rare, but have included local irritation, pain, itch, redness, acne, and rash. While other side effects are not expected and have not been seen in other studies of ruxolitinib cream, there is a potential risk of side effects

that have been observed with much higher doses of ruxolitinib when given by mouth. These risks include infection, low blood counts, liver inflammation, elevated cholesterol, dizziness, headache, fatigue, insomnia, diarrhea, and abdominal pain. As with any treatment, there is a small risk of an allergic reaction, though this has not been documented for ruxolitinib cream.

There is a risk of no change or worsening of disease, as would be true with any change in treatment.

FDA approved medication label information, risks include:

- Patients treated with oral JAK inhibitors for inflammatory conditions are at risk for developing serious infections that may lead to hospitalization or death
- Reported infections include:
 - Active tuberculosis (TB), which may present with pulmonary or extrapulmonary disease

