 - Invasive fungal infections (eg, candidiasis, pneumocystosis)
 - Bacterial, viral, and other infections due to opportunistic pathogens
- Avoid use in patients with an active, serious infection, including localized infections
- If a serious infection develops, interrupt therapy until infection is controlled
- Do not resume until the infection is controlled.
- Carefully consider the risks and benefits of treatment before initiating therapy in patients with chronic or recurrent infection
- Closely monitor for developing signs and symptoms of infection during and after treatment

Reproductive Risks

Women of childbearing potential will be counseled to use acceptable birth control methods. Women will not be allowed to participate in this study if they are pregnant, become pregnant, or are nursing an infant.

General Risks

When participating in any research study there is a possibility for invasion of privacy or breach of confidentiality. As with any research study, there may be additional risks that are unknown or unexpected. The subjects are advised to contact their study team with any questions and/or concerns. At that time the study team will determine whether or not any untoward medical occurrence is associated with the study and/or study drug and will be recorded on the Medical History and/or Adverse Event page of the source document.

Adverse Event Reporting

An adverse event (AE) is any observation whether or not considered to be product related, that is unfavorable and unintended and that occurs after any use of an investigational medicinal product.

Any observation of abnormality will be documented on the Adverse event form. The Investigator will document the date of occurrence, severity, resolution, and will assess the relationship of the adverse event to the study drug by assigning a causality assessment. Results from laboratory evaluations which are outside of the laboratory reference range will constitute an adverse event only if the Investigator determines that the result is clinically significant.

Severity will be assessed by the following system:

- Mild: easily tolerated, causing minimal discomfort
- Moderate: sufficiently discomforting to interfere with every day activities
- Severe: prevents normal every day activities

Serious Adverse Events (SAE)

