FDA definition: A serious adverse event results in death, is life-threatening, requires inpatient hospitalization or prolongation of existing hospitalization, results in persistent or significant disability / incapacity, results in a congenital anomaly / birth defect. Events fitting these descriptions will be considered adverse events if they occur after treatment with the study drug.

As soon as reasonably possible, subjects will contact the Investigator to report any unfavorable events. The Investigator will assess the case, determine the need for treatment, and consult with Incyte, Inc, particularly in the occurrence of:

- A serious adverse event.
- An unusual frequency of non-serious adverse events.
- Death, even if this does not appear to be related to therapy with the study drug.

The Investigator will notify the URMC Institutional Review Board within approximately 3 working days if a serious adverse event occurs.

SAE Reporting to Incyte

The Principal Investigator (PI) must report all Serious Adverse Events (SAEs) to Incyte within 24 hours of learning of an event, regardless of the PI's causality assessment. This notification should be provided on a completed Serious Adverse Event (SAE) form. SAE reporting for each subject begins the day the informed consent is signed by the patient and within 30 days after subject has completed or discontinued from the study or has taken last dose of the study drug, or as described in the protocol.

SAEs, occurring using Incyte study drug, are reported in accordance with the effective protocol. SAEs occurring with any other commercial drug are reported to the manufacturer of that drug in accordance with regulations and protocol.

Initial SAEs and/or subsequent follow-up reports should be reported via email to [contact] or fax [name]. SAE reports should be for a single subject. SAE forms should be sent with a cover sheet and any additional attachments.

All adverse event information is reported to Incyte on the Principal Investigator's/Institution's Adverse Event Report Form, or a CIOMS-I or MedWatch Form FDA 3500A, or on an Adverse Event Report Form which may be provided by Incyte upon request. The Principal Investigator does not provide medical records (e.g., discharge summary) to Incyte, unless specifically requested.

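### Patients who leave early, including those withdrawn because they need a prohibited treatment, have no required safety contact in the 30 days after last dose in which SAEs are reportable

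*Combined protocol and SAP*

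**What the plan says.** - **Prohibited treatment (section 4, Prohibited Medications and procedures).** Topical or systemic immunosuppressants and immunomodulators, phototherapy, and hand surgery or other procedures are not allowed. The paragraph ends: "If medically necessary, the investigator will withdraw the patients from the study". The wording is loose. In context it means that a medical need for one of the barred treatments leads to withdrawal.
- **Post-drug visit.** Section 4 lists "visit 5 – 112 +/- 3 days (16 weeks) safety follow up 4 weeks post treatment". Section 2 (Design & Methodology) shows where the date is counted from: "visit 5 post treatment follow up, 4 weeks (V5, 112+/- 3 days post V1".
- **Unscheduled visits (section 4).** They are recorded if performed. When one is held, the team must review side effects and concomitant medications and do a brief physical examination. Beyond that, "The remaining elements of the unscheduled visit are up to the discretion of the investigator".
- **SAE reporting (section 5, SAE Reporting to Incyte).** The period runs from consent to 30 days after completion, discontinuation or last dose. The 24-hour clock starts when the investigator learns of the event.
- **How events come to light (section 5).** "As soon as reasonably possible, subjects will contact the Investigator to report any unfavorable events". For a known event, "The Investigator will document the date of occurrence, severity, resolution, and will assess the relationship of the adverse event to the study drug".
- **Pregnancy.** Contraception counselling at Visit 1 covers the treatment period, "including 30 days after stopping study drug (16 weeks or 112 days". A urine pregnancy test is listed at Visit 5. Pregnancies are reportable to the drug supplier within 24 hours of discovery.
- **Outcomes and numbers.** Adverse events and use of rescue medications are secondary outcomes (sections 1 and 6). Up to 25 patients enrol so that 15 complete, and section 3 expects some early discontinuation.

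**The concern.** The plan makes SAEs reportable for 30 days after a patient stops, but it schedules a look into that period only for patients who treat to week 12. The reporting duties for SAEs and pregnancies are triggered by learning of the event, so they work only as well as the plan's means of learning.

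The patients left out are a foreseeable group. Entry requires an inadequate response to standard topical therapy, or that topical corticosteroids be inadvisable. Section 5 names worsening disease as a risk. Needing a barred treatment is therefore a natural reason to leave, and some of these patients may be starting an immunosuppressant as they go.

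What is at stake is the completeness of a secondary safety outcome in a study of at most 25 patients, and whether a pregnancy soon after stopping is noticed. No efficacy conclusion depends on it.

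**Working it through.** The plan states no figure for this point, so the check sets the visit calendar against the reporting period.

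**Inputs.** Visits at days 28, 56, 84 and 112, each +/- 3, counted from Visit 1 (section 4). SAE period of 30 days (section 5). Enrolment up to 25, with 15 completing (section 1).

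**1. Completer, taking last dose as Visit 4.**
- Visit 4 falls on days 81 to 87 and Visit 5 on days 109 to 115.
- Nominal gap: 112 - 84 = 28 days. Shortest: 109 - 87 = 22. Longest: 115 - 81 = 34.
- Of the 7 x 7 = 49 pairs of window days, the gap exceeds 30 days in 4 + 3 + 2 + 1 = 10. This counts pairs and is not a probability.
- Required scheduled contacts after last dose: 1, at about 4 weeks. It is not guaranteed to fall within 30 days.

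**2. Patient withdrawn from the study early.** Participation ends, so no later visit applies, and no visit or call is dated from last dose. Required scheduled contacts after last dose: 0, whatever the stopping day.

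**3. Would Visit 5 help if it were kept on its present date?** For a last dose on day 28, 42 or 56, day 112 is 112 - 28 = 84, 112 - 42 = 70 or 112 - 56 = 56 days later. All lie outside 30 days.

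**4. Would keeping the patient on the existing calendar be enough?** For a last dose on any day from 1 to 83, the next nominal visit is 1 to 28 days later, and 1 or 2 nominal visits fall within 30 days. The last of these can come as early as day 3 after last dose: stopping on day 81 gives 84 - 81 = 3, and the next visit is at 112 - 81 = 31. The calendar alone can therefore leave most of the period unobserved. A contact dated from last dose is needed.

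**5. Should the SAE period be changed?** For a completer it ends at 84 + 30 = day 114 if counted from last dose, and at 112 + 30 = day 142 if counted from completion, a difference of 28 days. A last-dose-only rule would shorten it, so it should stay as written.

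**6. Pregnancy.** For a completer, 84 + 30 = day 114, inside the Visit 5 window of days 109 to 115, so the contraception period and the Visit 5 test roughly coincide. A woman who leaves early has the same advice but no required test after drug.

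**The case against.** The strongest case against runs as follows. SAE reporting already covers discontinued patients, and they are told to report problems. If the decision to withdraw is taken at an off-schedule assessment, the unscheduled-visit rule already requires review of side effects and concomitant medications, because only the remaining elements are discretionary. Patients are recruited from the site's own dermatology clinics (section 7), so someone who leaves to receive dermatologic treatment may well be seen in the same department. The product is topical, and section 5 says of non-skin effects: "While other side effects are not expected and have not been seen in other studies of ruxolitinib cream". The event that triggers withdrawal is recorded, no off-drug laboratory tests are scheduled for anyone, and there is no comparison arm to bias.

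All of that stands, and it limits the size of the point. None of it is a required contact after last dose: nothing requires an unscheduled visit to take place, and routine care is incidental to the study. Section 5 also reproduces label advice to monitor for infection after treatment, but attaches no visit to it.

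Four stronger readings are tempting, and the documents do not support them:
- A reader might infer that SAEs after withdrawal are not reportable. They are, for 30 days.
- A reader might infer that self-report is the only route. Unscheduled visits and routine care are also possible.
- A reader might infer that up to 40% of patients are affected, from (25 - 15)/25. Ten is only the number of non-completers, for any reason, if 25 enrol and 15 complete. It does not forecast withdrawals.
- A reader might infer that the contraception advice fails for early stoppers. Thirty days after stopping holds for any stopping date, and day 112 is simply the completer's approximate date. Only the test is missing.

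In the plan's favour, one could read the label of 4 weeks post treatment as moving Visit 5 for early stoppers. Section 2 dates it from Visit 1, and a patient withdrawn from the study would not attend it in any case.

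**Conclusion.** The point holds and is worth correcting, though its effect is modest. Anyone who leaves the study early has 0 required scheduled safety contacts in the 30-day reporting period, against 1 for a completer at about 4 weeks. The gap is not peculiar to prohibited treatment: that rule is the clearest route into it, but the lack of any early-termination procedure applies to every early leaver.

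The number affected cannot be estimated from the documents. If 25 enrol, each such patient is 1/25 = 4% of the study.

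The conclusion rests on three assumptions: that withdrawal from the study means what it says, that a completer's last dose is at Visit 4, and that the protocol body is the whole schedule. The consent pages and appendix were not available, so instructions given to patients there cannot be judged.

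**What to change.** 1. In the prohibited-medications paragraph, replace withdrawal from the study with this rule: a medically necessary prohibited treatment may be given, study drug is then discontinued, and the patient stays in safety follow-up unless consent is withdrawn.
2. For every early discontinuation, whatever the reason, require a review of adverse events and concomitant medications at stopping, with a pregnancy test where applicable. Do this before the new therapy starts where possible.
3. For the same patients, require one contact about 30 days after last dose, asking about adverse events and pregnancy. Either a telephone call or Visit 5 without tape stripping will do.
4. List events that begin after the start of new therapy separately.
5. Leave the SAE reporting period unchanged.

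Recording IGA and HECSI at stopping is optional and not needed for this safety point.

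**Cost.** A protocol wording change, a short review at stopping (partly required already if an unscheduled visit is held), and one call or one USD 50 visit per early leaver. No blood draw or tape stripping is added. Some patients will refuse, and later events will be partly confounded by the new therapy, hence the separate listing.
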